## **15.6 Other Important PK Considerations**

• If data permits, the other PK parameters may be reported.

• If  $T_{last} = T_{max}$ ;  $C_{max}$  will not be reported for that Participant in the listings. It will be footnoted to indicate that sampling timepoints were not appropriate for that Participant.

### 15.7 Bioequivalence Analysis

The bioequivalence analysis will be conducted for  $C_{max}$ , AUC0-inf and AUC0-last. Additionally, the bioequivalence analysis will also be conducted for concentrations collected on Days 29±1 day and 57±3 days as well as for partial AUC up to 168 hours, Days 29±1 day and 57±3. Natural log-transformed PK parameter  $C_{max}$ , C29days, C57days, AUC0-last and AUC0-inf, AUC0-168h, and AUC up to Days 29 and 57 will be analysed using the general linear model with the treatment as fixed via PROC GLM in SAS. For the purpose of the analysis, a preliminary ANCOVA model including variables group, age, sex, BMI and weight will be performed. If variables age, sex, BMI or weight were to be significant in this analysis, these variables will be kept in the final analysis. Upon review of the immunogenicity analysis, secondary ANCOVA analysis including ADA as a categorical or numerical variable could be performed. The 90% confidence intervals of the geometric least square mean ratio of test and reference i.e., MB05 group means relative to the EU-Synagis group means will be obtained by back transformation.

The following comparisons will be done:

(1) MB05 as Test VS EU-Synagis® as Reference

(2) MB05 as Test VS US-Synagis® as Reference

(3) EU-Synagis® as Test VS US-Synagis® as Reference

Bioequivalence will be concluded for  $C_{max}$ ,  $AUC_{0-last}$ ,  $AUC_{0-inf}$  and additional parameters  $C_{29days}$ ,  $C_{57days}$  and partial areas  $AUC_{0-168h}$ ,  $AUC_{29days}$  and  $AUC_{57days}$  between test and refere, if the 90% CIs for the ratio of geometric least squares means are contained within the range 80.00% to 125.00%. However, for  $C_{max}$ , a wider range 70.00% to 143.00% could also be considered.

Protocol Number: MB05-A-01-21 Document Status: Final 2.0 Version date: 15-Jun-2023

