# 6.6 Randomisation and Blinding

### 6.6.1 Randomisation and Allocation to Treatment Arm

All study participants who sign an informed consent form will receive a unique sequential number (i.e., a screening number). Randomisation will be stratified based on the subject's body weight (50 to <75 kg and  $\geq$ 75 to 95 kg) and gender (male and female).

Participants who are deemed eligible to be dosed will be assigned a randomisation number in accordance with the study randomisation schedule. Each participant will be assigned to one of the following study treatment arms in a 1:1:1 allocation ratio:

- Arm A: MB05
- Arm B: EU-Synagis®
- Arm C: US-Synagis®

The allocation to Arm A, B or C will be performed using a block randomisation algorithm, and the randomisation schedule will be maintained under controlled access. If required, sealed participant-specific code break envelopes will be produced by the Sponsor (or a Sponsor delegate) and will be retained at the clinical facility in a secure, accessible location.

The personnel involved in the dispensing of study treatments will be accountable for ensuring compliance to the study randomisation schedule. The unblinded study Monitor will review the randomisation schedule in comparison to the dispensing log in order to verify correct randomisation.

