## **13.1** Sample Size Considerations

Up to a total number of 141 healthy subjects (male and female) are planned to be enrolled in

mAbxience Research SL

the study. Subjects who meet the entry criteria will be randomised to receive a single dose of MB05, EU-sourced Synagis® or US-sourced Synagis® in a 1:1:1 fashion. Randomisation will be stratified based on the subject's body weight (50 to <75 kg and  $\geq$ 75 to 95 kg) and gender (male and female). To achieve balance, the number of subjects enrolled in each stratum should be a multiple of 3, where possible.

The reported coefficients of variation (CVs) for AUC and  $C_{max}$  for Synagis® vary between 0.25 and 0.35. Based on a worst-case CV of 0.35 (Robbie et al., 2012), alpha of 0.05 (i.e., utilising a two-sided 90% CI around the mean difference) and a true hypothesised ratio for the mean difference of 0.95, a total of 141 subjects (47 subjects per arm respectively), 1:1:1 ratio) will provide approximately 85% power to demonstrate bioequivalence of MB05 with EU-sourced Synagis® and US-sourced Synagis®. Assuming a 5% dropout, a total of 132 evaluable subjects (44 subjects per arm) are sufficient for this measure.

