# 13.6.2 Serum Pharmacokinetic Parameters and Bioequivalence Analysis

Serum palivizumab concentrations from samples collected at specific timepoints following IM administration of each study treatment will be used to calculate PK parameters using non-

compartmental analysis methods. The following PK parameters will be determined:

- Cmax Maximum observed serum concentration obtained directly from the concentration versus time data.
- Tmax Time to maximum observed concentration, taken directly from the data. If the maximum serum concentration occurs at more than one time point, the first is chosen.
- kel Terminal elimination rate constant obtained from the slope of the line, fitted by linear least squares regression through the terminal points of the logarithmic concentration-time profiles.
- AUCt Area under the serum concentration-time curve from time zero to time t
- $t_{\frac{1}{2}}$  Apparent terminal half-life, calculated as  $t_{\frac{1}{2}} = \ln (2)/k_{el}$ .
- CL/F Apparent total serum clearance of drug after IM administration, where F is the fraction of drug absorbed, calculated as (Dose / AUC0-inf).
- $\label{eq:Vz/F} Vz/F \qquad \mbox{Apparent volume of distribution during terminal phase after IM} \\ administration, calculated as (CL/F / k_{el}).$

PK parameters for each participant will be listed and summarised by treatment using descriptive statistics.

Bioequivalence between MB05 and EU-Synagis®, between MB05 and US-Synagis® and between EU-Synagis® and US-Synagis® will be investigated for AUC0-inf and Cmax by analysis of variance using log-transformed PK parameter values. Bioequivalence will be assessed by calculating the 90% CIs for the ratio of the least squares geometric means for each pairwise comparison and each PK parameter. Bioequivalence will be concluded where the 90% CIs for the ratio of least squares geometric means are contained within the range 80.00% to 125.00%. For each pairwise treatment comparison and each PK parameter, this corresponds to undertaking two one-sided tests (TOST) of significance each at the 5% level.

Additional details of PK analysis will be provided in the study SAP.

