#### 9 DEMOGRAPHICS AND BASELINE INFORMATION

The demographics variables to be reported are listed below:

- Age (years) at baseline
- Sex
- Women of child-bearing potential
- Race
- Ethnicity
- Height (cm) at baseline
- Weight (kg) at baseline
- BMI (kg/m^2) at baseline

These variables will be summarized using descriptive statistics in accordance with Section 4.2 under the Safety Analysis Set for treatment groups defined in Section 4.6. Demographics variables will also be listed by treatment groups (Section 4.6) under the Safety analysis Set sorted by Participant ID.

The following baseline information analysis will be listed by treatment groups (Section 4.6) under the Safety analysis Set sorted by Participant ID.

- Urine Drug Screen
- Alcohol Breath Test
- Serology
- COVID-19 Test

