## **19.2** Final Analysis (End of Study)

The final analysis will be conducted after all Participants have completed the study, the clinical database has been locked, and the analysis populations have been approved prior to unblinding.

The final analysis will be based on the final version of the SAP. Any deviations from the planned analysis will be documented in the CSR.

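### SAP 15.7 selects the covariates of the primary bioequivalence model by an unspecified significance test on the PK data and does not require the randomisation factors, sex and body-weight stratum

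*SAP*

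**What the plan says.** Protocol 6.6.1: "Randomisation will be stratified based on the subject's body weight" (below 75 kg, or 75 kg and above) and on gender. Protocol 13.1 adds: "To achieve balance, the number of subjects enrolled in each stratum should be a multiple of 3, where possible". Protocol 13.6.2 plans an analysis of variance on log-transformed parameters, names no covariates or strata, and hands over to the SAP: "Additional details of PK analysis will be provided in the study SAP".

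SAP 15.7 says that the log-transformed parameters "will be analysed using the general linear model with the treatment as fixed via PROC GLM in SAS". Then "a preliminary ANCOVA model including variables group, age, sex, BMI and weight will be performed", followed by the retention rule: "If variables age, sex, BMI or weight were to be significant in this analysis, these variables will be kept in the final analysis". The same section covers eight parameters and three pairwise comparisons.

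SAP 2.1 (design) and SAP 3 (sample size) do not mention the stratification. SAP 1 promises that departures from the protocol's statistics will be given in section 18, and section 18 lists none.

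**The concern.** The model that produces the deciding confidence interval should be fixed before anyone sees the outcome. Here the candidate list is fixed, but the choice among candidates is made on the PK data that the final model will analyse. Four things are left open:

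- the significance level (the 5% in Protocol 13.6.2 belongs to the two one-sided tests of treatment);
- whether one covariate set applies to all parameters or each parameter gets its own;
- whether one significant covariate brings in all four or only itself;
- whether weight enters as a continuous value or as the 75 kg stratum.

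Two analysts following the text could report different primary intervals. The factors used to balance the arms may also be absent from the analysis, which makes the interval wider than necessary if those factors matter.

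**Working it through.** **1. Does anything elsewhere close the gap?** SAP 4.2 covers only how p-values are displayed. SAP 19.2 requires that "the clinical database has been locked, and the analysis populations have been approved prior to unblinding", but this protects the analysis populations, not the covariates. Protocol 13.6.2 defers to the SAP. The gap stands.

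**2. What does *group* mean?** SAP 2.1 defines dosing Groups 1 and 2, so the word is ambiguous. SAP 15.7 also speaks of MB05 group means, and *group* is missing from the list of terms that may be dropped. Both favour treatment group. On that reading the preliminary model needs unblinded data. On the other reading it could be run blinded, but still on the PK outcome.

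**3. The SAP's own power figure.** Inputs from SAP 3: CV 0.35, 45 per arm, true ratio 1, 90% CI within 80-125%.
- SD on the log scale = sqrt(ln(1 + 0.35²)) = 0.340
- SE = 0.340 × sqrt(2/45) = 0.0717
- CI half-width ≈ 1.662 × 0.0717 = 0.119, against ln(1.25) = 0.223
- Exact power of the two one-sided tests = 85.1%, which agrees with the stated 85%.

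**4. The rule against a fixed model, by simulation.** Assumptions: 135 subjects, blocks of 3 within sex × weight strata, weight limited to 50-95 kg, total CV 0.35, selection at p<0.05, sex-weight correlation 0.54, weight-BMI correlation 0.75. The share of log variance explained by the covariates is assumed. The fixed model here is treatment + sex + stratum + continuous weight. There were 60,000 trials per case.

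| Power (%) at ratio 1 | Rule | Fixed | Treatment only |
|---|---|---|---|
| Weight linear, 12% explained | 89.8 | 90.1 | 87.2 |
| Weight linear, 22% | 93.6 | 93.5 | 88.3 |
| Sex and weight share the effect, 12% | 89.5 | 90.0 | 87.7 |
| Sex and weight share the effect, 22% | 93.4 | 93.7 | 89.5 |

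In these cases, type I error at ratio 0.80 is 4.9-5.0% (rule), 5.0% (fixed) and 3.4-4.4% (treatment only). Over 27 scenarios (0, 12 or 22% explained; several effect shapes and weight-BMI correlations), fixed minus rule is -0.5 to +2.4 power points. Type I error is 4.3-5.4% for the rule and 4.7-5.3% for the fixed model. The gain is largest when the effect is a step at 75 kg; with no covariate effect the fixed model loses 0.2-0.5 points.

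A separate simulation (6,000 trials per case, sex and weight always in, 0 to 40% explained) gave fixed against rule 85.6 v 85.7%, 89.6 v 87.8%, 92.7 v 91.3% and 98.1 v 97.9%.

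**5. How often the factors are lost, and the cost when they are.** In step 4 the rule drops both sex and weight in about 25% of trials at 12% explained and 3.5% at 22%. In those trials its CI is about 3% wider (12%) or 5-6% wider (22%) than under the fixed model. Over all trials the difference is -0.3% to +0.9%. The drop rates are sensitive to assumptions: with weight linear at 12%, the rule keeps weight in 89.5, 73.5 and 57.3% of trials as the weight-BMI correlation goes from 0.5 to 0.75 to 0.85.

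**6. What the open wording allows.** Three readings (p<0.05; p<0.10; all four kept if any is significant) give different verdicts in 0.2-2.1% of trials. Taking the most favourable of the three gives type I error of 5.0-5.7%, against 4.5-5.3% for p<0.05 alone (Monte Carlo SE about 0.3 points). Taking the best of four models (treatment only, fixed, p<0.05, p<0.10) gives 5.4-5.9%.

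**The case against.** The candidate list is named in advance and includes sex and weight, so the stratification factors are not ignored. Once a level is written down the rule is mechanical, keeps type I error about nominal and costs little power. Dosing is already weight-adjusted at 3 mg/kg, so weight may explain little of the remaining variance; if it explains none, a fixed model loses slightly. All of this stands, and it limits the point to pre-specification.

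Three stronger readings are tempting but not supported.

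- *The rule inflates type I error.* At one fixed level it does not. The excess appears only if a reading is chosen after the results are seen, and nothing in the documents says that this will happen.
- *Dropping sex and weight widens the CI by 6% or 13%.* Those figures compare treatment-only with the fixed model over all trials: 0.1186/0.1117 = 1.06 at 12% explained and 0.1187/0.1051 = 1.13 at 22%. The SAP does not plan treatment-only in all trials. The rule tends to drop covariates when they look weak in that sample, so the loss is the smaller one in step 5.
- *The model will certainly be chosen unblinded.* That depends on what *group* means.

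**Conclusion.** The point holds as a gap in pre-specification of the primary analysis. The text defect is certain: no level, no rule for applying the selection across parameters or covariates, and no requirement to keep the randomisation factors. The covariates are settled after the PK outcome is seen and, on the likelier reading, after unblinding.

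The numerical effect is small. At a single fixed level, type I error is about nominal, and the fixed model with continuous weight shifts power by about -0.5 to +2.4 points. With a free choice among versions, type I error is about 5.0-5.9%. Where both factors are dropped, the CI is about 3% or 5-6% wider in the linear-weight and shared-effect cases. All of these figures rest on assumed covariate effects and correlations. The change is worth making because it is nearly free and removes a foreseeable dispute over the primary result.

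**What to change.** Delete the preliminary-ANCOVA sentences from SAP 15.7; the ambiguous *group* goes with them. State one model for every parameter and pairwise comparison:

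log(parameter) = treatment + sex + body-weight stratum as randomised (below 75 kg, or 75 kg and above), with all terms retained whatever their p-values.

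Continuous baseline weight may be added as a further prespecified term. It is optional, but the power range above is for the model that includes it. With weight linear at 22% explained, sex + stratum alone gives 91.3%, against 93.5% with continuous weight added and 93.6% for the rule.

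Report the treatment-only model, and a model adding age and BMI, as sensitivity analyses that do not decide bioequivalence. Record the move from the protocol's analysis of variance in SAP section 18.

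Cost: SAP wording only. SAP 9 already lists sex and "Weight (kg) at baseline"; the stratum has to be taken from the randomisation record. With 135 subjects and three arms, residual degrees of freedom fall from 132 to 130, or to 129 with continuous weight. If no covariate matters, the loss is at most about 0.5 power points. The sample size does not change.

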## 1 INTRODUCTION

This Statistical Analysis Plan (SAP) provides the outline for the statistical analysis of the data collected for MB05-A-01-21 titled: "FANTASY–A Randomised, Double-Blind, 3-arm Parallel Study to Compare the Pharmacokinetics, Safety, Immunogenicity and Tolerability of MB05 (Proposed Palivizumab Biosimilar), EU-sourced Synagis® and US-sourced Synagis®, Administered as a Single Dose Intramuscular Injection in Healthy Volunteers." (Version 2.0 dated 07 June 2022).

This SAP is written with consideration of the recommendations outlined in the International Council for Harmonisation (ICH) E9 guideline entitled, "Guidance for Industry: Statistical Principles for Clinical Trials" and the ICH E3 guideline entitled, "Guidance for Industry: Structure and Content of Clinical Study Reports.

The SAP will be finalized prior to database lock. Any deviations from the SAP after database lock, reasons for such deviations, and all alternatives or additional statistical analyses that may be performed will be described the Clinical Study Report (CSR).

If the SAP differs the statistical considerations in the protocol, details will be given in section 18.

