#### 2.2 **Objectives**

#### 2.2.1 **Primary Objectives and Endpoints**

#### The primary objective of this study is:

- To establish the bioequivalence between MB05 and EU-Synagis®, between MB05 and US-Synagis® and between EU-Synagis® and US-Synagis® up to Day 99, in terms of:
  - Area under the serum concentration versus time curve from time zero to infinity (AUC0-inf)
  - Maximum observed serum concentration (Cmax)

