# **18 CHANGES TO THE PLANNED ANALYSIS**

Not applicable.

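### SAP 15.7 leaves open whether Cmax, a primary parameter, is judged against 80.00%–125.00% or 70.00%–143.00%

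*SAP*

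**What the plan says.** Cmax and AUC0-inf are the two parameters in the primary objective and endpoint (Protocol 5.1 and 6.7.1; SAP 2.2.1).

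Protocol 13.6.2 gives one rule for both: "Bioequivalence will be concluded where the 90% CIs for the ratio of least squares geometric means are contained within the range 80.00% to 125.00"%. It equates this with "two one-sided tests (TOST) of significance each at the 5% level", separately by comparison and by parameter. It makes no exception for Cmax.

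SAP 15.7 first states the same criterion for all its parameters, Cmax included: "if the 90% CIs for the ratio of geometric least squares means are contained within the range 80.00% to 125.00"%. The next sentence opens with a contrast and adds that, for Cmax, "a wider range 70.00% to 143.00% could also be considered".

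SAP section 1 says where departures from the protocol belong: "If the SAP differs the statistical considerations in the protocol, details will be given in section 18". The whole text of section 18 is "Not applicable".

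**The concern.** The added sentence directly follows the rule for concluding bioequivalence and qualifies it, so on its face it offers a second way for Cmax to pass. Four things are missing:

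- a condition for using the wider range, such as a threshold on observed variability;
- a justification for it;
- a statement of which range governs if the two disagree;
- a time by which the choice must be made. SAP 19.2 requires the analysis populations to be approved before unblinding, but says nothing about the acceptance range.

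Finalising the SAP before database lock does not close the gap, because the open choice sits inside the final SAP. If the 90% CI for Cmax falls outside 80.00%–125.00% but inside 70.00%–143.00%, the document supports either conclusion. The 5% error rate that the protocol attaches to its limits would then no longer describe the Cmax decision. The departure from the protocol is also undeclared by the SAP's own standard.

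**Working it through.** **Inputs.** CV 0.25 to 0.35, with 0.35 as the planning value (Protocol 13.1; SAP 3). 45 evaluable per arm and a true ratio of 1 (SAP 3). One-sided 5% tests, i.e. a 90% CI (Protocol 13.6.2). Limits 80.00%–125.00% and 70.00%–143.00% (SAP 15.7).

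**Formulas.** On the log scale, SD = √ln(1 + CV²) and SE = SD·√(2/n). Bioequivalence is concluded if ln(observed ratio) ± t(0.95, df)·SE, with SE estimated from the data, lies inside the log limits. The probability of that is computed exactly, by integrating over the chi-square distribution of the variance estimate. Here df = 2(n − 1) = 88.

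**Step 1: reproduce the plan's own figure.** At CV 0.35, SD = √ln(1.1225) = 0.340 and SE = 0.340·√(2/45) = 0.0717. With a true ratio of 1 and 80.00%–125.00%, power is 85.2% (85.4% with three-arm pooled df). This matches the SAP's approximate 85%. With 70.00%–143.00% the same inputs give 99.9%, and about 18 per arm would already reach 85%. The SAP's sample-size section names no limits, but its figure fits only the narrow range.

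**Step 2: which observed ratios pass.** With t = 1.662, the half-width is 1.662 × 0.0717 = 0.119, a factor of e^0.119 = 1.127. With the estimated SD equal to the planning SD:

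- 80.00%–125.00%: 0.80 × 1.127 = 0.90 to 1.25 / 1.127 = 1.11
- 70.00%–143.00%: 0.70 × 1.127 = 0.79 to 1.43 / 1.127 = 1.27

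**Step 3: error rate.** The narrow range lies wholly inside the wide one, so passing on either is the same as passing on 70.00%–143.00%. The probability of concluding bioequivalence on Cmax, in one pairwise comparison with 45 per arm, is:

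| True Cmax ratio | CV | 80.00%–125.00% | 70.00%–143.00% |
|---|---|---|---|
| 0.80 | 0.35 | 5.0% | 58.1% |
| 0.80 | 0.25 | 5.0% | 81.8% |
| 1.25 | 0.35 | 5.0% | 58.6% |
| 1.25 | 0.25 | 5.0% | 82.3% |
| 0.75 | 0.35 | 0.6% | 24.5% |
| 0.75 | 0.25 | 0.2% | 37.2% |

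Three-arm pooled df (132) moves these by about 0.2 percentage points at most (58.3% and 82.0% at ratio 0.80). With 44 or 47 per arm, the CV 0.35 figure at ratio 0.80 is 57.3% or 59.7%.

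**The case against.** The strongest reply is that the wider range may be meant only as supportive. The SAP first gives 80.00%–125.00% as the rule for concluding bioequivalence, and the wording that follows is permissive. On that reading the error rate at a true ratio of 0.80 stays at 5%. The reading is possible, but nothing in the SAP says so, and the sentence qualifies the conclusion rule itself. It also remains an inference that the range would be chosen after seeing the result. Both sets of limits are written down in advance; what is not fixed is which one governs.

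Second, the table covers Cmax alone. AUC0-inf is also primary and keeps 80.00%–125.00%. The documents do not say that both must pass. If they must, the joint error depends on the true AUC ratio. Take a true Cmax ratio of 0.80, the wide range governing, 45 per arm, equal CVs, and a Cmax–AUC correlation between 0 and 0.8 (an assumption; the documents give none). The chance that both pass is:

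- at most 5% if the true AUC ratio is 0.80;
- about 29% to 43% if it is 0.90 (CV 0.35);
- about 50% (CV 0.35) or 81% (CV 0.25) if it is 1.00.

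So AUC0-inf protects the overall claim when exposure also differs, and hardly at all when only the peak does.

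Third, the protocol leaves further PK detail to the SAP and allows its statistics section to be revised. Widening the acceptance range of a primary parameter is more than detail, though, and the SAP has its own section for recording such a change.

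A rationale may exist in documents not seen here. The upper limit is also not the exact reciprocal of 0.70 (1/0.70 = 142.86%), but this is trivial and carries no weight.

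**Conclusion.** The concern holds. The protocol and the SAP give different acceptance criteria for a primary parameter. The SAP does not say which governs and does not declare the difference.

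If the wider range decides, the chance of concluding bioequivalence on Cmax at the edge of the protocol's range goes from 5% to between about 58% and 82% over the documents' own CV range. These figures assume log-normal data, 45 evaluable per arm, an unadjusted treatment comparison, and one parameter in one pairwise comparison. If the wider range is purely supportive there is no inflation, but the text does not establish that. This must be fixed, because the success criterion for half of the primary endpoint is undetermined as written.

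**What to change.** Delete the sentence in SAP 15.7 that admits 70.00%–143.00%. State that Cmax, like AUC0-inf, is concluded bioequivalent only if its 90% CI lies within 80.00%–125.00%, as in Protocol 13.6.2. This restores the protocol's rule with no further work and matches the basis of the stated power.

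Two alternatives would also leave a single governing rule:

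- keep the wider range but label it supportive, with no part in the conclusion;
- if it is meant to govern, amend the protocol with a justification and a condition fixed before unblinding, and record the change in SAP section 18.

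Deletion costs one sentence in a SAP revision. The sponsor gives up a fallback for Cmax that these documents do not justify. The documents do not show whether unblinding has taken place. If it has, the clinical study report should base the Cmax conclusion on 80.00%–125.00% and present any result on the wider range as not pre-specified for decision.
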